2.9 Evaluation of *AURKA* Polymorphisms and Response to Aurora A Kinase Inhibition

The gene encoding Aurora A kinase, *AURKA*, contains two missense polymorphisms with minor allele frequencies greater than 10%: rs1047972 (18% minor allele frequency) and rs2273535 (30% minor allele frequency). Several studies have evaluated a potential role for these and other *AURKA* polymorphisms in the risk of developing a range of cancers, with mixed results[25-,28]. In addition, there is some evidence that the presence of *AURKA* polymorphism may impact the clinical behavior of breast or gastric cancer [29,30]. To date, only one small study has described the impact of *AURKA* polymorphisms on toxicity and pharmacokinetics of a pan-Aurora kinase inhibitor, with negative findings [31]. It remains unclear whether *AURKA* polymorphisms might be associated with response to a specific Aurora A kinase inhibitor. An optional correlative study will involve evaluation of two common *AURKA* missense polymorphisms and response to protocol therapy.

2.10 Summary and Rationale for Clinical Use of MLN8237 with Irinotecan and Temozolomide

The combination of irinotecan and temozolomide is well-tolerated and provides a modest degree of anti-tumor activity in heavily pre-treated patients. The toxicity profile and activity level suggest that this combination may serve as a useful platform onto which novel compounds may be added. MLN8237 demonstrates compelling single-agent activity in preclinical models of neuroblastoma. Aurora A kinase inhibition results in at least additive cytotoxicity when used in combination with other chemotherapy agents. This trial therefore will evaluate MLN8237 added to irinotecan and temozolomide. While both irinotecan and MLN8237 are metabolized via *UGT1A1*, neither drug has been shown to induce or inhibit *UGT1A1*. Patients in the phase I portion of this trial will have detailed pharmacokinetic assessment of irinotecan and MLN8237 levels. Optional studies include assessment of *UGT1A1* and *AURKA* polymorphisms and tumor Aurora A expression levels.

2.11 Rationale for Amendment #3

The protocol initially opened to enrollment using protocol version Amendment #2. Six patients enrolled to dose level 1. Two patients experienced protocol-defined dose-limiting toxicities during the first cycle of therapy. One patient developed grade 3 mucositis, prolonged grade 4 neutropenia, and treatment delay due to ongoing thrombocytopenia, in addition to grade 3 dehydration, anorexia and febrile neutropenia. The other patient had treatment delay due to ongoing neutropenia. In addition, three of six patients experienced grade 3 diarrhea in dose level 1. In dose level 1, the use of myeloid growth factor support and cephalosporin diarrhea prophylaxis were not mandated. After review of the toxicity profile seen in dose level 1, the study committee determined that further development of this combination should include mandatory myeloid growth factor support and cephalosporin diarrhea prophylaxis. Amendment #3 makes this change and resumes evaluation of this combination with dose level 1B that uses the same doses of MLN8237, irinotecan, and temozolomide as evaluated in dose level 1, but with mandatory supportive care measures.

2.12 Rationale for Amendment #5

Amendment #4 was an administrative amendment.

Amendment #5 designates the recommended phase 2 dose for this regimen when used with enteric coated tablets. After Amendment #3, dose levels 1B, 2B, and 3B were evaluated in the phase 1 portion of the study. At dose level 1B, 0 / 6 patients had first-course DLT. At dose level 2B, 1 / 6 patients had first-course DLT (prolonged grade 4 neutropenia). At dose level 3B, 2 / 4 evaluable patients had first-course DLT (prolonged grade 4 neutropenia; failure to meet platelet criteria by Day 35 of course 1). This experience established the recommended phase 2 dose as dose level 2B when used with MLN8237 enteric coated tablets. With Amendment 5, the phase 2 portion of the study is open to patients who are able to swallow intact pills. Patients on the phase 2 portion will begin therapy at dose level 2B and will utilize the enteric coated tablet formulation.

Amendment #5 also adds a cohort of patients treated with an MLN8237 oral solution. This new solution will provide access to patients who are unable to swallow intact pills. The pharmacokinetics of an oral solution formulation of MLN8237 was evaluated in 17 adult patients who participated in a cross-over relative bioavailability study evaluating both the powder-in-capsule formulation (with similar bioavailability to the current enteric coated tablet formulation) and the oral solution. The geometric mean ratios (oral solution in reference to the powder-in-capsule) for exposure (AUC_{inf}) and peak plasma concentration (C_{max}) were determined as 1.26 (90% CI 1.09-1.47) and 1.90 (1.52-2.37), respectively (Investigator Brochure). Based upon these results, pediatric patients receiving single-agent MLN8237 as the oral solution are recommended to receive $60 \text{ mg/m}^2/\text{dose}$ instead of the standard pediatric dose of 80 mg/m^2 obtained with intact pills. In the context of the current combination regimen in which the recommended phase 2 MLN8237 dose with enteric coated tablets is $60 \text{ mg/m}^2/\text{dose}$, patients in the oral solution cohort will begin therapy at dose level 1B with 45 mg/m^2 MLN8237. Patients in this cohort will exclusively receive the oral solution and will be required to participate in pharmacokinetic testing.

Amendment #5 also changes the dose modification procedures to utilize the existing dose levels rather than using 25% dose reductions. This change will facilitate dose rounding in a more uniform manner based upon the existing protocol dosing nomograms.

Amendment #5 also updates NANT response criteria, including criteria for evaluable disease.

2.13 Rationale for Amendment #6

Experience with this regimen prior to Amendment #6 has demonstrated that hematologic toxicity is the primary dose-limiting toxicity (DLT). However, some DLTs have been uncomplicated grade 4 neutropenia for > 1 week (to date, one episode in course 1 in the phase II portion in the absence of other DLT) or uncomplicated thrombocytopenia requiring platelet transfusions more than twice in a 1 week period (to date, one episode in course 1 in the phase II portion in the absence of other DLT). Having grade 4 neutropenia for > 1 week or need for multiple platelet transfusions during a nadir is consistent with the degree of hematologic toxicity seen in other common regimens used for patients with newly diagnosed high-risk neuroblastoma and in some regimens used in patients with relapsed disease. Therefore, with Amendment #6, these elements of the definition of hematologic DLT are removed. Hematologic DLT will be defined solely on the basis of delays in starting subsequent courses beyond day 36 due to failure to recover counts. Day 36 has been updated from Day 35, as that would be a true two week delay, and allowing for patients to stay on a Monday start schedule.

Prior to Amendment #6, the statistical design allowed up to 6 patients from the phase I portion of the trial to contribute to the phase II portion of the trial. Given early evidence of activity of this regimen, there is a desire to complete a full independent phase II evaluation of this regimen. Amendment #6 formally separates the phase I and phase II portions of the study and will require an additional 6 patients evaluable for response. Patient accrual to the phase II portion has been rapid, such that enrolling an additional 6 patients is feasible.

Amendment #6 also updates eligibility and response criteria for uniformity with other current active NANT clinical trials. The consent form and drug information section have been updated to include updated risk tables based upon the most recent MLN8237 Investigators Brochure. Additional minor edits are also included.

2.14 Rationale for Amendment #7

This amendment reflects the change of institution for [name], Study Chairperson and IND holder, from University of California, San Francisco to Dana-Farber Cancer Institute. An additional update to NANT participating sites includes a change in Principal Investigator for Hospital for Sick Children, Toronto from [name] to [name].

2.15 Rationale for Amendment #8

This amendment reflects the change in NANT Site Principal Investigator for Seattle Children's Hospital from [name] to [name]; the change in NANT Site Principal Investigator for Lucile Packard Children's Hospital from [name] to [name]; and the change in NANT Site Principal Investigator for C.S. Mott Children's Hospital from [name] to [name]. This also includes the removal of Memorial Sloan Kettering Cancer Center as a participating site.

3.0 PATIENT ELIGIBILITY CRITERIA AND REGISTRATION

3.1 Patient Preparation for Study Entry and Registration

Patient Registration On Study:

Eligible patients will be registered by contacting the NANT Operations Center at Children's Hospital Los Angeles Monday through Friday, 8:30am – 5:00 pm Pacific Time at [contact] except holidays. The information requested on the N2009-03 Demographic, Eligibility, and On Study Forms must be completed, and the signed informed consent along with the documentation confirming eligibility must be FAX'd to [contact] for registration to occur. Each patient will be assigned a unique NANT registration and study subject number. The dose level will be assigned by the NANT Operations Center at the time of study registration. Once eligibility is verified, the NANT Operations center will send an email confirming registration which must be received prior to starting any protocol therapy or the patient will be declared ineligible. This email will also assign the dose level, and will be sent to the treating facility, Study Chair, and Study Vice-Chair. A registration worksheet is available on the web site (www.NANT.org) in the data forms packet to assist institutions with registration requirements for this protocol.

Contact Person: Research Coordinator
NANT Operations Center
Children's Hospital Los Angeles
[name]
Los Angeles, CA 90027
[contact]
[contact]

To allow non-English speaking patients to participate in this study, bilingual health services will be provided in the appropriate language when feasible.

Patients are required to start protocol therapy within 1 week of study enrollment. The start of protocol therapy is defined as the start of oral cephalosporin in Day -1. Protocol therapy must not start until the patient has been enrolled.

Co-enrollment on NANT 2004-05 (Neuroblastoma Biology Study) is strongly encouraged.

Important note: The eligibility criteria listed below are interpreted literally and cannot be waived.

3.2 Inclusion Criteria

3.2.1 Age

Patients must be \geq 12 months and \leq 30 years of age when registered on study.

3.2.2 Diagnosis

Patients must have a diagnosis of neuroblastoma either by histologic verification of neuroblastoma and/or demonstration of tumor cells in the bone marrow with increased urinary catecholamines.

3.2.3 Disease Stage/risk group

Patients must have high-risk neuroblastoma according to COG risk classification at the time of study enrollment. Patients who were initially considered low or intermediate risk, but were then reclassified as high risk are also eligible.

3.2.4 Response to Prior Therapy (using INRC definitions):

3.2.4.1 Recurrent/progressive disease at any time prior to enrollment – regardless of response to frontline therapy.

3.2.4.2 **Refractory disease:** persistent sites of disease after achieving a best overall response of no response to frontline therapy after a minimum of 4 cycles of induction therapy AND patient has never had recurrent/progressive disease.

3.2.4.3 **Persistent disease:** persistent sites of disease after achieving a best overall response of partial response to frontline therapy after a minimum of 4 cycles of induction therapy AND patient has never had recurrent/progressive disease.

3.2.5 Sites of Disease

Patients must have at least ONE of the following (lesions may have received prior radiation therapy as long as they meet the other criteria listed below):

3.2.5.1 Bone disease

At least one MIBG avid bone site or diffuse MIBG uptake.

- a. For recurrent/progressive or refractory disease, a biopsy is not required regardless of number of MIBG avid lesions.
- b. For persistent disease, if patient has only 1 or 2 MIBG avid lesions OR a Curie Score of 1-2, then biopsy confirmation of neuroblastoma and/or ganglioneuroblastoma in at least one site present at the time of enrollment (bone marrow, bone, or soft tissue) is required to be obtained at any time point prior to enrollment and two weeks subsequent to most recent prior therapy. If a patient has 3 or more MIBG avid lesions OR a Curie Score of ≥ 3 then no biopsy is required for eligibility.
- c. If tumor is known to be MIBG non-avid, then a patient must have at least one FDG-PET avid bone site present at the time of enrollment with biopsy confirmation of neuroblastoma and/or ganglioneuroblastoma obtained at any time prior to enrollment and two weeks subsequent to most recent prior therapy.

3.2.5.2 Any amount of neuroblastoma tumor cells in the bone marrow based on routine morphology (with or without immunocytochemistry) in at least one sample from bilateral aspirates and biopsies.

3.2.5.3 At least one soft tissue lesion that meets criteria for a TARGET lesion as defined by:

- a. **SIZE:** Lesion can be accurately measured in at least one dimension with a longest diameter $\geq 10\text{mm}$, or for lymph nodes $\geq 15\text{mm}$ on short axis. Lesions meeting size criteria will be considered measurable.
- b. **In addition to size, a lesion needs to meet ONE of the following criteria:**
 - i. **MIBG avid.** For patients with persistent disease only: If a patient has only 1 or 2 MIBG avid lesions OR a Curie Score of 1 – 2, then biopsy confirmation of neuroblastoma and/or ganglioneuroblastoma in at least one site present at time of enrollment (either bone marrow, bone and/or soft tissue) is required to be obtained at any time point prior to enrollment and at least two weeks subsequent to most recent prior therapy. If a patient has 3 or more MIBG avid lesions OR a Curie Score of ≥ 3 then no biopsy is required for eligibility.
 - ii. **FDG-PET avid (only if tumor known to be MIBG non-avid).** These patients must have had a biopsy confirming neuroblastoma and/or ganglioneuroblastoma in at least one FDG-PET avid site present at the time of enrollment done prior to enrollment and at least two weeks subsequent to the most recent prior therapy.
 - iii. **Non-avid lesion (both MIBG and FDG-PET non-avid).** These patients must have had a biopsy confirming neuroblastoma and/or ganglioneuroblastoma in at least one non-avid lesion present at the time of enrollment done prior to enrollment and at least two weeks subsequent to the most recent prior therapy.

3.2.6 Ability to Swallow Pills

MLN8237 enteric coated tablets must be swallowed as whole tablets. Therefore, patients must be able to swallow pills to be eligible for the phase 2 portion of the study. Patients who are unable to swallow pills are eligible for the oral solution cohort.

3.2.7 Performance level

Patients must have a Lansky (\leq 16 years) or Karnofsky ($>$ 16 years) score of at least 50 (Appendix I).

3.2.8 Prior Therapy

Patients must have fully recovered from the acute toxic effects of all prior chemotherapy, immunotherapy, or radiotherapy prior to entering this study.

Myelosuppressive chemotherapy and/or biologics: Last dose of any myelosuppressive therapy and/or biologics was given at least 3 weeks before the start date for therapy on this protocol.

Radiation: Last dose of radiation was given \geq 2 wks for local palliative XRT (small port); \geq 6 weeks for prior MIBG therapy; \geq 6 months must have elapsed if prior TBI or if \geq 50% radiation of pelvis; \geq 6 wks must have elapsed if other substantial BM radiation.

Patients will be excluded if they have received craniospinal radiation.

For patients with only one site of measurable or evaluable disease, radiation must not have been given to that site unless that site still has MIBG uptake or demonstrated clear progression after radiation, or a biopsy of the site demonstrated neuroblastoma at least 2 weeks after the last day of radiation.

Stem Cell Transplant (SCT): Patients are eligible 12 weeks after myeloablative therapy with autologous stem cell transplant (timed from start of protocol therapy). Patients must meet adequate bone marrow function definition (see organ function requirements, below) post-myeloablative therapy. Patients who received stem cell reinfusion following non-myeloablative therapy are eligible once they meet peripheral blood count criteria in 3.2.10.1.

Patients status post-allogeneic stem cell transplant are excluded.

Prior MLN8237, Irinotecan, and Temozolomide

Patients who have received prior MLN8237 are excluded from all phases of the study.

Patients previously treated with irinotecan and/or temozolomide will be eligible if they have not had documented progressive disease during treatment with a regimen containing these agents.

Growth factor(s): All cytokines or myeloid growth factors must be discontinued a minimum of 7 days prior to the start of protocol therapy.

3.2.9 Concomitant Therapy Restrictions

- a. Patients must not be receiving any other anti-cancer agents or radiotherapy at the time of study entry or while on study.
- b. Patients must not be receiving other investigational medications (covered under another IND) within 30 days of study entry or while on study.
- c. Patients must not be receiving cyclosporine, digoxin, tacrolimus, or sirolimus (p-glycoprotein substrates)
- d. Patients must not be receiving scheduled benzodiazepine (such as lorazepam or diazepam) therapy. Use of as-needed benzodiazepines is allowed, though discouraged.

3.2.10 Organ Function Requirements

3.2.10.1 Hematologic Function:

Patients must meet the following hematologic criteria for enrollment onto the oral solution cohort of the study regardless of bone marrow disease status:

- a. ANC: $\geq 1000/\mu\text{L}$ (no hematopoietic growth factors within 7 days of the start date of protocol therapy); and
- b. Platelet count: $\geq 100,000/\mu\text{l}$, transfusion independent (no platelet transfusions within 1 week of the start date of protocol therapy).

Patients with bone marrow disease who meet the above count criteria will be eligible to enroll in the oral solution cohort of the study and will be evaluable for hematologic toxicity.

Patients must meet the following hematologic criteria for enrollment onto the phase 2 portion of the study unless they have bone marrow disease:

- a. ANC: $\geq 1000/\mu\text{L}$ (no hematopoietic growth factors within 7 days of the start date of protocol therapy); and
- b. Platelet count: $\geq 100,000/\mu\text{l}$, transfusion independent (no platelet transfusions within 1 week of the start date of protocol therapy).

Patients with bone marrow involvement on the phase 2 portion of the study must meet the following hematologic criteria. These patients will not be evaluable for hematologic toxicity or hematologic DLT:

- a. ANC $\geq 750/\mu\text{L}$ (no hematopoietic growth factors within 7 days of the start date of protocol therapy); and
- b. Platelet count $\geq 50,000/\mu\text{L}$ (platelet transfusions allowed).

3.2.10.2 Renal Function:

Patients must have adequate renal function defined as age-adjusted serum creatinine $\leq 1.5 \times$ normal for age (see below):

Age	Maximum Allowable Serum Creatinine
≤ 5 years	0.8 mg/dL
> 5 and ≤ 10 years	1.0 mg/dL
> 10 and ≤ 15 years	1.2 mg/dL
> 15 years	1.5 mg/dL

3.2.10.3 Liver Function:

- a. Total bilirubin $\leq 1.5 \times$ normal for age;
- b. SGPT (ALT) ≤ 135 U/L ($\leq 3 \times$ ULN) for the oral solution cohort and ≤ 225 ($\leq 5 \times$ ULN) for the phase 2 portion of the study. Note that for ALT, the upper limit of normal for all sites is defined as 45 U/L.

3.2.10.4 Reproductive Function:

All post-menarchal females must have a negative serum or urine beta-HCG. Female subject must either be post-menopausal or surgically sterilized or willing to use an acceptable method of birth control (ie, a hormonal contraceptive, intra-uterine device, diaphragm with spermicide, condom with spermicide, or abstinence) for the duration of the study. Male subject must agree to use an acceptable method for contraception during the entire study treatment period through 4 months after the last dose of MLN8237.

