4.0 TREATMENT PROGRAM

4.1 Treatment Overview

Cycle of Treatment

Prior to the start of each cycle of therapy, patients must meet organ function requirements listed in section 3.2.10, with the exception of platelet and ANC criteria which differ from entry criteria:

- Patients in any portion of the study entering the study with platelets \geq 100,000/uL (transfusion independent) and ANC \geq 1000/uL must recover to platelets \geq 75,000/uL (transfusion independent) and ANC \geq 750/uL (off any myeloid growth factors for more than 24 hours) prior to the start of the next cycle of therapy. Patients in the phase 2 portion entering the study with bone marrow disease and platelets $<$ 100,000/uL or ANC $<$ 1000/uL must recover to platelets \geq 50,000/uL (with transfusions) and ANC \geq 750/uL (off any myeloid growth factors for more than 24 hours) prior to the start of the next cycle.

Disease evaluation will take place during the third week of cycles 2, 4, 8, and then every 4 cycles. Patients may receive up to 34 cycles of therapy (~2 years) on study in the absence of dose-limiting toxicity (DLT) or progressive disease. Decisions regarding additional therapy on this study will be made by the study chair and treating physician in collaboration with the vice chair and sponsor.

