4.6 Dose Modification

4.6.1 Thrombocytopenia

Patients evaluable for hematologic toxicity who develop dose-limiting thrombocytopenia (per section 4.4) should have their dose of temozolomide reduced to 75 mg/m^2 (see Appendix IIIB).

Patients who continue to have dose-limiting thrombocytopenia despite temozolomide dose reduction should have a bone marrow evaluation to exclude progressive bone marrow metastatic disease. In the absence of progressive bone marrow disease, these patients should have their dose of MLN8237 reduced by one dose level. Patients already receiving dose level -1B or an absolute dose of MLN8237 of 10 mg and who require dose reduction will be removed from protocol therapy.

Patients with recurrent dose-limiting thrombocytopenia despite dose reductions in both MLN8237 and temozolomide will undergo up to one additional dose reduction of MLN8237 and temozolomide. Temozolomide will be reduced first followed by MLN8237 in the next cycle if the combination continues to result in dose limiting thrombocytopenia. The dose of temozolomide should be reduced to $50 \text{ mg/m}^2/\text{dose}$, with dose rounded down to the nearest 5 mg. The dose of MLN8237 should be reduced by an additional dose level. Patients already receiving dose level -1B or an absolute dose of MLN8237 of 10 mg and who require dose reduction will be removed from protocol therapy.

Patients with recurrent dose-limiting thrombocytopenia despite two dose reductions in both MLN8237 and temozolomide will be removed from protocol therapy.

Patients who are not evaluable for hematologic toxicity due to low counts and bone marrow involvement at study entry who develop dose limiting thrombocytopenia should undergo bone marrow re-evaluation. If the bone marrow does not show progressive disease, then the dose modification strategy above should be followed.

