4.6.2 Neutropenia

Patients who have dose-limiting neutropenia despite myeloid growth factor support should have their dose of temozolomide reduced to 75 mg/m^2 (see Appendix IIIB). These patients should continue to receive myeloid growth factor support.

Patients who continue to have dose-limiting neutropenia despite myeloid growth factor support and temozolomide dose reduction are encouraged to undergo bone marrow evaluation to exclude progressive bone marrow metastatic disease. In the absence of progressive bone marrow metastatic disease, these patients should have their dose of MLN8237 reduced by one dose level. These patients should continue to receive myeloid growth factor support. Patients already receiving dose level -1B or an absolute dose of MLN8237 of 10 mg and who require dose reduction will be removed from protocol therapy.

Patients with recurrent dose-limiting neutropenia despite myeloid growth factor support and dose reductions in both MLN8237 and temozolomide will undergo up to one additional dose reduction of MLN8237 and temozolomide in increments of 25% of the starting dose of each agent. Temozolomide will be reduced first followed by MLN8237 in the next cycle if the combination continues to result in dose limiting neutropenia. The dose of temozolomide should be reduced to 50 mg/m²/dose, with dose rounded down to the nearest 5 mg. The dose of MLN8237 should be reduced by an additional dose level. Patients already receiving dose level -1B or an absolute dose of MLN8237 of 10 mg and who require dose reduction will be removed from protocol therapy.

Patients with recurrent dose-limiting neutropenia despite myeloid growth factor support and two dose reductions in both MLN8237 and temozolomide will be removed from protocol therapy.

Patients who are not evaluable for hematologic toxicity due to low counts and bone marrow involvement at study entry should undergo bone marrow re-evaluation if they develop dose-limiting neutropenia. If the bone marrow does not show progressive disease, then the dose modification strategy above should be followed.

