Patients who enrolled as inevaluable for hematologic DLT due to marrow involvement and low baseline blood counts will remain inevaluable for hematologic DLT even if their bone marrow disease appears to improve on therapy. The number of these patients who require dose modifications in subsequent courses will be reported descriptively. These patients will follow dose modification guidelines according to sections 4.6.1 and 4.6.2. These patients will be evaluable for response.

The table below summarizes the probability that the boundary indicating excessive DLT's has been crossed according to the rules above. The values in the table below are based on 10,000 simulations and are accurate to ± 0.01 (based on a 95% confidence interval).

Table: Probability that the boundary indicating excessive DLT's has been crossed							
True Chance of DLT	5%	10%	15%	20%	25%	30%	35%
Probability of Excessive DLT's	0.04	0.13	0.28	0.44	0.61	0.75	0.85

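### Section 3.2.10.1 excludes every phase 2 patient with marrow involvement from hematologic DLT evaluation, while 4.6.1, 4.6.2 and 10.4 describe that group as also having low baseline counts

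*Combined protocol and SAP*

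**What the plan says.** Section 3.2.10.1 sets the standard phase 2 entry counts (ANC at least 1000/µL, platelets at least 100,000/µL without transfusion) and exempts patients with marrow disease. The next paragraph begins "Patients with bone marrow involvement on the phase 2 portion of the study must meet the following hematologic criteria", gives lower limits (ANC 750/µL, platelets 50,000/µL with transfusion allowed), and adds "These patients will not be evaluable for hematologic toxicity or hematologic DLT". It does not mention patients who have marrow disease but whose counts meet the standard limits. For the oral solution cohort the same section does address them. It says "Patients with bone marrow disease who meet the above count criteria will be eligible to enroll in the oral solution cohort of the study" and that they are evaluable for hematologic toxicity.

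Other sections bring in counts:

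- 10.4: "Patients who enrolled as inevaluable for hematologic DLT due to marrow involvement and low baseline blood counts" stay inevaluable even if the marrow improves.
- 4.6.1: "Patients who are not evaluable for hematologic toxicity due to low counts and bone marrow involvement at study entry who develop dose limiting thrombocytopenia" have the marrow re-evaluated before dose modification.
- 4.6.2, for neutropenia that becomes dose-limiting: "Patients who are not evaluable for hematologic toxicity due to low counts and bone marrow involvement at study entry should undergo bone marrow re-evaluation".
- 4.1: entrants to any portion with normal counts must recover to platelets of 75,000/µL and ANC of 750/µL before the next cycle. The relaxed platelet limit is for "Patients in the phase 2 portion entering the study with bone marrow disease and platelets" below 100,000/µL or ANC below 1000/µL.

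**The concern.** Consider a phase 2 patient with tumor in the marrow, ANC 3000/µL and platelets 200,000/µL. Such patients are plausible: under 3.2.5.2 any amount of tumor in one marrow sample is a qualifying disease site, and that need not depress the counts. Section 3.2.10.1, read as written, makes this patient inevaluable for hematologic DLT. The joint reason given in 4.6.1, 4.6.2 and 10.4 does not cover the patient.

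This matters because 2.13 names hematologic toxicity as the regimen's primary DLT. Since Amendment 6, hematologic DLT means failure to meet the restart counts by day 36 (2.13, 4.4). Section 4.1 gives this patient a definite restart threshold, so the DLT can be determined, yet under 3.2.10.1 it would not count toward the 10.4 review triggers or the reported first-course DLT rate. Two analysts could derive different DLT numerators from the same data, and describing toxicity is a primary aim (1.2).

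**Working it through.** **Reproducing the plan's table.** Section 10.4 triggers a review at 2 DLTs in the first 6 patients, 3 in 9, 4 in 12, 5 in 15, 6 in 18, or 7 in all. I took the last as 7 in 20, the phase 2 maximum. With DLT probability p per patient, the number of DLTs is carried forward patient by patient as a binomial count, and paths at or above the boundary are removed at each look. For example, the first look at p = 0.30 gives 1 − 0.7^6 − 6 × 0.3 × 0.7^5 = 1 − 0.118 − 0.303 = 0.58.

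| True DLT rate | 5% | 10% | 15% | 20% | 25% | 30% | 35% |
|---|---|---|---|---|---|---|---|
| Stated in 10.4 | 0.04 | 0.13 | 0.28 | 0.44 | 0.61 | 0.75 | 0.85 |
| Recomputed | 0.035 | 0.130 | 0.268 | 0.429 | 0.592 | 0.734 | 0.844 |

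All values agree within 0.02. The table is consistent with a model in which every enrolled patient can register any DLT.

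**Effect if affected patients stay in the denominators.** Let f be the share of phase 2 patients who are marrow-positive with normal counts, H the first-course hematologic DLT rate and O the rate of other DLTs. The documents give none of these, so all are assumptions. If hematologic DLTs in the fraction f are not counted, the countable rate is O + H × (1 − f). For H = 25%, O = 5%, f = 20% this is 0.05 + 0.25 × 0.8 = 0.25.

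| H + O | f = 0 | f = 20% | f = 40% |
|---|---|---|---|
| 25% + 5%: countable rate | 30% | 25% | 20% |
| review probability | 0.73 | 0.59 | 0.43 |
| 10% + 5%: countable rate | 15% | 13% | 11% |
| review probability | 0.27 | 0.21 | 0.15 |
| 5% + 5%: countable rate | 10% | 9% | 8% |
| review probability | 0.13 | 0.11 | 0.09 |

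**Effect if affected patients leave the denominators.** With f = 20% or 40%, 16 or 12 of 20 patients are counted. At a 30% DLT rate the review probability goes from 0.73 to 0.71 (16 counted, looks at 6, 9, 12 and 15) or 0.69 (12 counted, looks at 6, 9 and 12). The expected DLT rate among those counted stays at 30%, assuming the subgroup has the same rate.

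**Dose-modification text.** Section 4.6.1 opens with patients evaluable for hematologic toxicity and closes with those inevaluable because of low counts together with marrow involvement. A patient who is inevaluable under 3.2.10.1 but has normal counts fits neither paragraph. The opening of 4.6.2 has no evaluability condition, so no such gap arises for neutropenia.

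**The case against.** The best defence is that the disputed sentence stands in the paragraph that introduces the relaxed entry counts, so it can be read as meaning only patients who enter under that relaxation. On that reading 3.2.10.1 agrees with 4.1, 4.6.1, 4.6.2 and 10.4, and section 10.4 already holds the wording wanted for monitoring. The reading is possible, but the text does not secure it: the standard limits are lifted for marrow disease as such, and the oral solution paragraph singles out count-normal patients where the phase 2 paragraph does not.

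Three further objections hold, and each rules out something that a reader might infer.

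- **Two express, opposite classifications.** No section states that a phase 2 marrow-positive patient with normal counts is evaluable. That follows only from the two-part reason in 4.6.1, 4.6.2 and 10.4 and from the split by counts in 4.1.
- **Marrow re-evaluation first.** One might infer that classification under 3.2.10.1 sends these patients to re-evaluation before dose modification. The 4.6.1 paragraph requires low counts, so it does not reach them. The thrombocytopenia route is undefined.
- **A fall from 0.73 to 0.43 as the established loss.** It needs a 25% hematologic DLT rate that nothing in the documents supports under the current definition. The one DLT in six at dose level 2B was prolonged grade 4 neutropenia (2.12), a criterion that Amendment 6 removed. The two isolated phase 2 episodes cited in 2.13 also met only removed criteria. The figure also depends on keeping these patients in the denominators.

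The boundary prompts a formal review and does not stop the trial. Toxicity is reported for all patients who begin MLN8237 (10.2.1, 10.6.1), and course 1 toxicity and hemogram forms are submitted weekly (12.0). Hematologic events in these patients therefore stay visible even if they do not count toward a trigger.

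**Conclusion.** The inconsistency is real and worth correcting, though its numerical effect cannot be fixed from the documents. Section 3.2.10.1 uses marrow involvement alone, whereas the sections that apply the classification also use counts. The literal reading lowers the sensitivity of the review triggers whenever the subgroup is not empty and hematologic DLTs occur in it.

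With these patients kept in the denominators and f between 20% and 40%, the loss in review probability runs from 0.02–0.04 at 5% plus 5% DLT to 0.14–0.30 at 25% plus 5%. With them left out, it is 0.02–0.04 at 30% DLT, mainly because fewer patients are counted. No stated figure becomes wrong: the 10.4 table reproduces under its own model.

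**What to change.** For phase 2 DLT monitoring and reporting only, amend the sentence in 3.2.10.1 to match 10.4: a patient is inevaluable for hematologic DLT only with marrow involvement and a baseline ANC below 1000/µL or platelets below 100,000/µL. Record each patient's status at registration, before cycle 1, since 10.4 keeps that status fixed afterwards.

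Separately, the sponsor must reconcile 3.2.10.1 with the two thrombocytopenia paragraphs of 4.6.1, which leave marrow-positive patients with normal counts without a stated route. No clinical rule is proposed here.

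The cost is one sentence and one field on the eligibility form. Blood counts and marrow results are already required for eligibility and faxed at registration (7.1, footnote 4). The downside is that the reported first-course DLT rate may be slightly less favourable.
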